4.4 Analysis of Efficacy

The analysis of primary and secondary efficacy variables will be based on the initial assessment.

4.4.1 Primary Efficacy Endpoint

4.4.1.1 Primary Efficacy Endpoint Definition

The primary efficacy endpoint is the mean whole mouth BI score at Week 3.

The BI will be assessed for the facial and lingual/palatal gingival surfaces of all evaluable teeth, six sites per tooth (mesiobuccal, buccal, distobuccal, mesiolingual/palatal, lingual/palatal and distolingual/palatal). Gingival bleeding is assessed 30 seconds after probing. Assessments will be performed one quadrant at a time; BI scores will be recorded before moving to the next quadrant. The BI will be assessed by the same examiner on all evaluable teeth at Baseline (Visit 2), Week 2 (Visit 3) and Week 3 (Visit 4). The BI scoring system will be as follows:

Table 4-2 The Bleeding Index (BI)

Score	Description
0	Absence of bleeding on probing
1	Bleeding observed within 30 seconds of probing
2	Bleeding observed immediately on probing

The mean whole mouth BI score for each subject will be derived from the total BI score divided by the number of tooth sites scored.

4.4.1.2 Statistical Hypothesis, Model, and Method of Analysis

Descriptive statistics (n, mean, SD, SE, median, minimum, maximum) of the primary variable will be provided at Baseline, Week 2 and Week 3 visits by study product group for the m-ITT population ([Table 14.2.2.1](#)).

The primary analysis is a comparison of the mean whole mouth BI score between the test dentifrice and negative control dentifrice at Week 3 for subjects eligible for the m-ITT population.

The null hypothesis for the primary endpoint is that there is no difference in the mean BI score between the 2 study product groups.

H₀: $\mu_1 = \mu_2$

The alternative hypothesis is that there is a difference in the mean BI score between the 2 study product groups.

H₁: $\mu_1 \neq \mu_2$

The mean BI score will be analyzed using analysis of covariance (ANCOVA) with study product group, gender, and baseline MGI stratification as factors and baseline mean BI score as a covariate. Adjusted means and their SEs, for each study product group will be displayed with the study product group difference, SE, 95% confidence interval (CI) of the difference, between-product p-value and percent difference between study product groups in [Table 14.2.2.2](#) for m-ITT population.

Percent difference will be calculated as:

- Percent Difference = (Adjusted Mean Difference/Adjusted Mean of Negative Control Dentifrice)*100.

All statistical tests of hypotheses will be two-sided and will employ a level of significance of $\alpha = 0.05$.

This study will be considered successful if a statistically significant difference between the adjusted mean BI scores of the two study product groups at Week 3 is observed to be in favor of the test dentifrice (SnF₂ dentifrice).

The assumption of normality and homogeneity of variance in the ANCOVA model will be investigated. Violation of this assumption will be overcome using a suitable data transformation or a non-parametric technique (e.g. Van Elteren test).

The raw mean and SE of the BI score for each study product group will be presented graphically over time for the m-ITT population in [Figure 14.2.1](#).

The BI obtained for each tooth, surface and site will be listed by subject and visit in [Listing 16.2.6.1](#) for all randomized subjects. The mean whole mouth BI score will be listed by subject and visit in [Listing 16.2.6.4](#) for all randomized subjects.

4.4.1.3 Supportive Analyses

If there is more than 10% difference in the overall number of subjects between PP and m-ITT populations, a summary of the primary efficacy variable will be presented for all subjects in the PP population ([Table 14.2.2.3](#)) and the same ANCOVA model applied to the primary analysis will be performed on the PP population ([Table 14.2.2.4](#)).

4.4.2 Secondary Efficacy Variables

4.4.2.1 Mean BI at Week 2

The mean BI score at Week 2 will be calculated in the same way as stated in [Section 4.4.1.1](#).

4.4.2.2 Number of Bleeding Sites at Week 2 and Week 3

The number of bleeding sites (NBS) will be derived from BI , where a bleeding site is a site scored as 1 or 2. The BI scoring system is described in [Section 4.4.1.1](#).

4.4.2.3 Modified Gingival Index at Week 2 and Week 3

The MGI will be assessed for the facial and lingual/palatal gingiva of all evaluable teeth, four sites per tooth (facial surface - papilla and margin; lingual/palatal surface - papilla and margin).

The MGI scoring system will be as described in [Table 4-3](#) and will be assessed by the same examiner on all evaluable teeth at Baseline (Visit 2), Week 2 (Visit 3) and Week 3 (Visit 4).

Table 4-3 The Modified Gingival Index

Score	Description
0	Absence of inflammation
1	Mild inflammation: slight change in colour, little change in texture of any portion of the marginal or papillary gingival unit
2	Mild inflammation: criteria as [1] but involving the entire marginal or papillary gingival unit
3	Moderate inflammation: glazing, redness, edema, and/or hypertrophy of the marginal or papillary gingival unit
4	Severe inflammation: marked redness, edema and/or hypertrophy of the marginal or papillary gingival unit, spontaneous bleeding, congestion, or ulceration

The mean whole mouth MGI score for each subject will be derived from the total MGI score divided by the number of tooth sites scored.

4.4.2.4 Turesky Plaque Index (Overall and Interproximal) at Week 2 and Week 3

Supra-gingival plaque will be assessed on the facial and lingual surfaces of the teeth using the TPI. Each tooth surface will be divided into three areas; three scores will be recorded facially (mesiofacial, facial, distofacial) and three scores lingually (mesiolingual, lingual and distolingual) generating a total of six scores per tooth. The plaque will be disclosed and scored for each site as follows.

Table 4-4 Turesky Plaque Index

Score	Description
0	No plaque
1	Separate flecks of plaque at the cervical margin
2	Thin continuous band of plaque (up to 1 mm) at the cervical margin
3	Band of plaque wider than 1 mm but covering < 1/3 of the tooth surface
4	Plaque covering \geq 1/3 but < 2/3 of the tooth surface
5	Plaque covering \geq 2/3 of the tooth surface

The mean Overall TPI score for each subject will be derived from the total TPI score over all tooth sites divided by the number of tooth sites scored.

The mean Interproximal TPI score for each subject will be derived from the total TPI score over all interproximal tooth sites divided by the number of interproximal tooth sites scored.

4.4.3 Handling of Missing Values/Censoring/Discontinuations

Missing data will not be replaced or imputed. Subjects who withdraw from the study early will be included in the statistical analysis up to the point of withdrawal. Subjects who withdraw will not be replaced.

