4.1 Populations for Analysis

4.1.1 Subject Disposition

Screen failures are defined as subjects who consent to participate in the clinical study but are not subsequently randomized. An enrolled subject is a subject who has signed informed consent and is eligible to proceed beyond the screening visit.

The number of subjects screened, enrolled and randomized will be presented in [Table 14.1.1](#). The number and percentage of screen failure subjects (subjects not randomized) with reasons why subjects are not randomized will also be displayed. Percentages for screen failure subjects will be based on the total number of subjects screened.

The number and percentage of subjects who complete and discontinue the study, broken down by reason for discontinuation, will be presented by study product group and overall in [Table 14.1.1](#). The percentages will be based on the number of subjects randomized.

[Table 14.1.1](#) will also present the number and percentage of subjects in each of the defined analysis populations by study product group and overall. Percentages will be based on the number of subjects randomized in the relevant study product group or overall.

Subject disposition including demographic data (age, sex and race), screening date, study product start date and time, the subject status (completer, Yes/No), study completion/withdrawal date, duration (in days) in the study (defined as [(date of completion or withdrawal – study product start date) + 1]), the primary reason for withdrawal and further details for withdrawal will be listed ([Listing 16.2.1.1](#)).

Subject disposition information will be listed for non-randomized subjects ([Listing 16.2.1.2](#)), including demographic information (age, sex and race), screening date, reason for screen failure and any further details of reason for screen failure.

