4.1.3 Analysis Populations

The analysis populations defined for this study are as follows:

Table 4-1 Analysis Populations

Population	Definition/Criteria	Analyses Evaluated
Safety	
 All randomized subjects who receive at least one dose of the study product. 
This population will be based on the study product the subject actually received.
	Safety
Modified Intent-To-Treat (m-ITT)	
 All randomized subjects who received at least one dose of the study product and provided at least one post-baseline assessment of efficacy (BI, MGI or TPI). 
All m-ITT population summaries and analyses will be presented according to the study product randomized.
	Efficacy
Per Protocol (PP)	
 All subjects included in the m-ITT population who have at least one assessment of efficacy (BI, MGI or TPI) considered unaffected by protocol violations. 
Subjects with a protocol violation that is deemed to affect efficacy for only some (but not all) of the efficacy assessments will be part of the PP population.
 
Protocol deviations that would exclude subjects from the PP population are defined in Section 4.1.2 (Protocol Deviations).
	Efficacy analyses for BI score
Repeatability	
 Comprise of all subjects who have a repeat clinical assessment of efficacy (R) at any visit. There will be a separate population for repeat MGI assessment and repeat TPI assessment: 
 MGI Repeatability population: Subjects with at least one initial and repeat assessment of MGI at any visit. 	Repeatability analyses

Population	Definition/Criteria	Analyses Evaluated
	
 TPI Repeatability population: Subjects with at least one initial and repeat assessment of TPI at any visit. 	

The primary population for assessment of efficacy will be the m-ITT Population. A PP analysis will be performed only on the primary variable (BI score) if more than 10% of subjects in the m-ITT population are excluded from the PP Population.

Any repeat clinical data collected for the repeatability assessment will only be used to assess repeatability. The main assessment of efficacy will be based on the initial assessment.

Subjects excluded from any of the analysis populations will be listed in [Listing 16.2.3.1](#).

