4.5.1 Efficacy (Secondary)

4.5.1.1 Mean BI at Week 2

The mean BI score at Week 2 will be analyzed in the same way as stated in [Section 4.4.1.2](#).

4.5.1.2 Number of Bleeding Sites at Week 2 and Week 3

Descriptive statistics (n, mean, SD, SE, median, minimum, maximum) of the NBS will be provided by visit and randomized study product group for the m-ITT population ([Table 14.2.3.1](#)).

The NBS will be analyzed using ANCOVA with study product group, gender, and baseline MGI stratification as factors and baseline NBS as a covariate. Adjusted means and their SEs for each study product group will be displayed along with the study product group difference, SE, 95% CI of the difference, between-product p-value and percent difference between study product groups in [Table 14.2.3.2](#) for m-ITT population.

The assumption of normality and homogeneity of variance in the ANCOVA model will be investigated. Violation of this assumption will be overcome using a suitable data transformation or a non-parametric technique (e.g. Van Elteren test).

The raw mean and SE of the NBS for each study product group will be presented graphically over time for the m-ITT population in [Figure 14.2.2](#).

Bleeding sites will be listed in [Listing 16.2.6.1](#) for all randomized subjects. The NBS will be listed by subject and visit in [Listing 16.2.6.4](#) for all randomized subjects.

4.5.1.3 Mean MGI at Week 2 and Week 3

Descriptive statistics (n, mean, SD, SE, median, minimum, maximum) of the mean MGI score will be provided by visit and randomized study product group for the m-ITT population ([Table 14.2.4.1](#)).

The mean MGI score will be analyzed using ANCOVA with study product group and gender as factors and baseline mean MGI score as a covariate. Adjusted means and their SEs for each study product group will be displayed with the study product group difference, SE, 95% CI of the difference, between-product p-value and percent difference between study product groups in [Table 14.2.4.2](#) for m-ITT population.

The assumption of normality and homogeneity of variance in the ANCOVA model will be investigated. Violation of this assumption will be overcome using a suitable data transformation or a non-parametric technique (e.g. Van Elteren test).

The raw mean and SE of the MGI score will be presented graphically over time by study product group for the m-ITT population in [Figure 14.2.3](#).

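### Does the primary Week 3 BI test need a prespecified sensitivity analysis for missing scores?

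*SAP*

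**What the plan says.** SAP 4.4.1.2 compares mean BI between the two dentifrices "at Week 3 for subjects eligible for the m-ITT population", using ANCOVA with product group, gender and MGI stratum as factors and baseline BI as covariate. Protocol 12.2.5 gives the same model. On missing data, SAP 4.4.3 says "Missing data will not be replaced or imputed", and protocol 12.2.9 agrees. Early withdrawers contribute until they leave, which in practice means to the Week 2 analyses.

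Membership of m-ITT (SAP 4.1.3) needs only one efficacy score after baseline, on any of the three indices and at either visit. The per-protocol (PP) set keeps m-ITT subjects "who have at least one assessment of efficacy (BI, MGI or TPI) considered unaffected by protocol violations". The one supportive analysis of the primary endpoint, in SAP 4.4.1.3, is the same ANCOVA on PP, and it is conditional: "If there is more than 10% difference in the overall number of subjects between PP and m-ITT populations".

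Several planned outputs bear on loss:
- Table 14.2.2.1 gives n for BI by visit and product group.
- Table 14.1.1 gives, by product group: "The number and percentage of subjects who complete and discontinue the study, broken down by reason for discontinuation".
- Listing 16.2.6.4 covers subject-level data: "The mean whole mouth BI score will be listed by subject and visit in" that listing.
- SAP 4.5.1.1 covers the earlier visit: "The mean BI score at Week 2 will be analyzed in the same way as stated in" section 4.4.1.2.

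The list of data displays in Attachment 1 is not available, so the absence of a sensitivity analysis can be asserted only for the SAP text.

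**The concern.** Success rests on one significance test, and that test uses only subjects with a Week 3 score. If subjects with more bleeding leave one arm preferentially after Visit 3, those who remain flatter that arm. Nothing in the plan estimates how far this could move the Week 3 difference. The PP rerun does not help: it is the same model, and a subject with a valid Week 2 score stays in PP, so a missing Week 3 score alone never triggers it.

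Arm-dependent loss cannot be ruled out. Protocol 4.2 concedes that the products are not identical and that only the examiner is blind. At stake would be an overstated treatment difference, or a significant result that depends on who failed to return.

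**Working it through.** **Inputs from SAP 1.4:** difference 0.1 BI, SD 0.17, two-sided 5%, 90% power, 65 randomized and 60 evaluable per arm, 0.1 equal to about 23%. I read evaluable as having a Week 3 BI. No dropout rate is stated; the implied allowance is (65 − 60)/65 = 7.7% per arm.

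**The plan's own figure.** n = 2 × (0.17/0.1)² × (1.960 + 1.282)² = 60.7, so 61 per arm. Power with 60 is 89.7% (normal) or 89.2% (t). The stated 60 for 90% is reproduced to rounding.

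**Direct bias.** If a share p of an arm is missing and those subjects differ from observed peers by s, the observed mean is off by p × s. With 5/65 missing in each arm and a shift in the test arm only (s assumed):
- s = 0.05: 0.077 × 0.05 = 0.004
- s = 0.10: 0.008
- s = 0.17 (one SD): 0.013

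An equal shift in both arms cancels.

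**Simulation.** Assumptions, none from the documents: normal scores, 65 per arm, SD 0.17, baseline correlation 0.5, Week 2–Week 3 correlation 0.6 or 0.8, no true difference. Selective loss means that the chance of leaving rises about 2.7-fold per SD of Week 2 BI. There were 12,000 trials per row, so an error rate near 5% has Monte Carlo SE √(0.05 × 0.95/12,000) = 0.2 points. Positive bias favours the test product. Each pair is for correlation 0.6 / 0.8.

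| Loss per arm | Bias | Two-sided error | Error favouring test |
|---|---|---|---|
| 3 before and 2 after Visit 3, random | −0.0001 / 0.0001 | 5.0% / 5.5% | – |
| Same counts, test arm loses high scorers | 0.0019 / 0.0037 | 4.7% / 5.1% | 2.7% / 3.3% |
| Same counts, opposite selection in the two arms | 0.0036 / 0.0060 | 5.2% / 5.9% | 3.3% / 4.3% |
| All 5 after Visit 3, test arm loses high scorers | 0.0048 / 0.0071 | 5.6% / 5.6% | 4.0% / 4.2% |
| All 5 after Visit 3, opposite selection | 0.0093 / 0.0143 | 6.4% / 8.6% | 5.2% / 8.0% |

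A repeat of the selective 3-before, 2-after rows gave 0.0025 to 0.006 and 5.4% to 5.6%, against 4.8% to 5.3% under random loss. If instead control loses its high scorers and the true difference is 0.10, the bias runs toward no difference (−0.0016 / −0.0030 with 2 late losses).

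**Tipping point.** A shift s in 5 missing test subjects moves the difference by s × 5/65, holding the SE fixed.
- SD 0.17 as stated: critical difference = 1.980 × 0.17 × √(2/60) = 0.0615. Observed 0.10: (0.10 − 0.0615)/(5/65) = 0.50 BI. Observed 0.07: 0.11 BI.
- If 0.17 is a raw SD and the baseline correlation is 0.5: SE = 0.17 × √0.75 × √(2/60) = 0.0269, critical difference 0.053. Observed 0.10: 0.61 BI. Observed 0.07: 0.22 BI.

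For scale, 0.1/0.23 implies means of about 0.435 for control and 0.335 for test. A 0.50 shift puts the missing test subjects at about 0.835, well above the control mean.

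**Missing test subjects scored as control.** The shift then equals the observed difference D, which shrinks to D × 60/65: 0.10 becomes 0.092 and 0.07 becomes 0.065, both still above 0.0615. Only results between 0.0615 and 0.0615 × 65/60 = 0.0666 would be overturned (0.053 to 0.058 with the adjusted SD).

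**The case for a change.** The best argument for acting is that it costs little: a paragraph in the SAP and two short analyses on BI already scored at Weeks 2 and 3. A check fixed before unblinding carries more weight than one chosen afterwards, and the comfort above depends on a dropout allowance that is only implied. If all 10 losses fell in the test arm, simulated bias with no true difference reaches 0.012 (two-sided error 7.35%) when loss follows Week 2 BI, and 0.019 (12.1%) when it follows the unseen Week 3 score (4,000 trials, Week 2–Week 3 correlation 0.7).

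What stands is that a borderline result, or loss of that lopsided kind, would deserve a supplementary analysis. But the documents do not point to such loss: the tubes are overwrapped to hide branding (protocol 6.1.1), and only about one week separates Visits 3 and 4. Lopsided loss would also show in Tables 14.1.1 and 14.2.2.1.

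The obvious remedy has limits too. A repeated-measures model removes bias only where loss depends on observed scores. In the last example above it leaves 0.013 of the 0.019. It recovers nothing after baseline for subjects lost before Visit 3, who are outside m-ITT; covering them needs a delta-adjusted check on all randomized subjects.

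**Conclusion.** No change follows. The protocol and SAP agree on the endpoint, the model and the rule against imputation, and the primary analysis and success criterion would be the same with or without an added check. At the implied loss of up to 5 of 65 per arm, bias is about zero if loss is random or alike in both arms. It is about 0.002 to 0.006 BI under assumed arm-specific selection with 2 of 5 losses after Visit 3, at most 6% of the 0.1 design difference. At an observed 0.10 the result withstands a shift of 0.50 to 0.61 BI in the missing test subjects; at 0.07 the range is 0.11 to 0.22.

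This rests on the implied loss, on my assumed correlations and selection strength, and on reading evaluable as having a Week 3 score. It would weaken if loss were much larger, fell almost wholly in one arm, or the result were near the significance limit. The number with Week 3 BI by arm is already planned, and analysts can add a mixed model and a delta-adjusted check from data in hand. That is a sensible option rather than a correction.

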4.5 Analysis of Secondary Objectives

Each secondary variable will be analyzed separately as per the primary variable ([Section 4.4.1.2](#)). All analyses will be conducted on the m-ITT population only. For the analysis of MGI the stratification factor of MGI will not be included as the baseline value of MGI is included as a covariate.

4.5.1 Efficacy (Secondary)

4.5.1.1 Mean BI at Week 2

The mean BI score at Week 2 will be analyzed in the same way as stated in [Section 4.4.1.2](#).

4.5.1.2 Number of Bleeding Sites at Week 2 and Week 3

Descriptive statistics (n, mean, SD, SE, median, minimum, maximum) of the NBS will be provided by visit and randomized study product group for the m-ITT population ([Table 14.2.3.1](#)).

The NBS will be analyzed using ANCOVA with study product group, gender, and baseline MGI stratification as factors and baseline NBS as a covariate. Adjusted means and their SEs for each study product group will be displayed along with the study product group difference, SE, 95% CI of the difference, between-product p-value and percent difference between study product groups in [Table 14.2.3.2](#) for m-ITT population.

The assumption of normality and homogeneity of variance in the ANCOVA model will be investigated. Violation of this assumption will be overcome using a suitable data transformation or a non-parametric technique (e.g. Van Elteren test).

The raw mean and SE of the NBS for each study product group will be presented graphically over time for the m-ITT population in [Figure 14.2.2](#).

Bleeding sites will be listed in [Listing 16.2.6.1](#) for all randomized subjects. The NBS will be listed by subject and visit in [Listing 16.2.6.4](#) for all randomized subjects.

4.5.1.3 Mean MGI at Week 2 and Week 3

Descriptive statistics (n, mean, SD, SE, median, minimum, maximum) of the mean MGI score will be provided by visit and randomized study product group for the m-ITT population ([Table 14.2.4.1](#)).

The mean MGI score will be analyzed using ANCOVA with study product group and gender as factors and baseline mean MGI score as a covariate. Adjusted means and their SEs for each study product group will be displayed with the study product group difference, SE, 95% CI of the difference, between-product p-value and percent difference between study product groups in [Table 14.2.4.2](#) for m-ITT population.

The assumption of normality and homogeneity of variance in the ANCOVA model will be investigated. Violation of this assumption will be overcome using a suitable data transformation or a non-parametric technique (e.g. Van Elteren test).

The raw mean and SE of the MGI score will be presented graphically over time by study product group for the m-ITT population in [Figure 14.2.3](#).

The MGI obtained for each tooth, surface and site will be listed by subject and visit in [Listing 16.2.6.2](#) for all randomized subjects. The mean whole mouth MGI score will be listed by subject and visit in [Listing 16.2.6.4](#) for all randomized subjects.

4.5.1.4 Mean TPI (Overall) at Week 2 and Week 3

Descriptive statistics (n, mean, SD, SE, median, minimum, maximum) of the mean Overall TPI score will be provided by visit and randomized study product group for the m-ITT population ([Table 14.2.5.1](#)).

The mean Overall TPI will be analyzed using ANCOVA with study product group, gender, and baseline MGI stratification as factors and baseline mean Overall TPI score as a covariate. Adjusted means and their SEs for each study product group will be displayed with the study product group difference, SE, 95% CI of the difference, between-product p-value and percent difference between study product groups in [Table 14.2.5.2](#) for m-ITT population.

The assumption of normality and homogeneity of variance in the ANCOVA model will be investigated. Violation of this assumption will be overcome using a suitable data transformation or a non-parametric technique (e.g. Van Elteren test).

The raw mean and SE of the Overall TPI score for each study product group will be presented graphically over time for the m-ITT population in [Figure 14.2.4](#).

The TPI obtained for each tooth, surface and site will be listed by subject and visit in [Listing 16.2.6.3](#) for all randomized subjects. The mean Overall TPI score will be listed by subject and visit in [Listing 16.2.6.4](#) for all randomized subjects.

4.5.1.5 Mean TPI (Interproximal) at Week 2 and Week 3

Descriptive statistics (n, mean, SD, SE, median, minimum, maximum) of the mean Interproximal TPI score will be provided by visit and randomized study product group for the m-ITT population ([Table 14.2.6.1](#)).

The mean Interproximal TPI will be analyzed using ANCOVA with study product group, gender, and baseline MGI stratification as factors and baseline mean Interproximal TPI score as a covariate. Adjusted means and their SEs for each study product group will be displayed with the study product group difference, SE, 95% CI of the difference, between-product p-value and percent difference between study product groups in [Table 14.2.6.2](#) for m-ITT population.

The assumption of normality and homogeneity of variance in the ANCOVA model will be investigated. Violation of this assumption will be overcome using a suitable data transformation or a non-parametric technique (e.g. Van Elteren test).

The mean Interproximal TPI score will be listed by subject and visit in [Listing 16.2.6.4](#) for all randomized subjects.

